3.3. Randomization

All 40 HFs part of the DYNAMIC project and using ePOCT+ for the first time during the second phase of the project (i.e. 20 HFs that were in the control group during the first phase of DYNAMIC, and 20 HFs newly included for the second phase) will be included in the medAL-mentor study. HFs will be randomized (1:1, intervention:control) to have access to medAL-mentor (intervention) or routine monitoring (control). Randomization will be stratified by number of patients/week (< or > 25 children under five per week) and by access to GoT-HoMIS (the Tanzanian Health Management Information System), to ensure balance of these variables in the two arms. Where possible, the exposure will be randomized 1:1 within strata and misfits will be reallocated to strata to get as good as possible overall balance (i.e. similarity between the two arms).¹⁸

An independent statistician will perform the randomization.

3.4. Timing of final analysis

Final analysis will be performed after collection of the outcome for 6 months in all 40 HFs included in the study (30 November 2023). All outcomes will be analysed collectively.

3.5. Timing of outcome assessments

The primary and secondary outcomes will be assessed with data recorded by the HCW at the time of the consultation (day 0).

4. Statistical principles

All applicable statistical tests will be 2-sided and will be performed using a 5% significance level. All confidence intervals presented will be 95% and two-sided.

4.1. Adherence and protocol deviations

Adherence to the medAL-mentor study protocol is assessed based on the percentage of :

Intervention HFs with :

- Access to medAL-mentor for HCWs and the study team
- Regular supportive messages (at least every 2 weeks) to HCW with feedbacks from medAL-mentor

- Targeted phone calls and visits based on medAL-mentor

Control HFs with :

- No access to medAL-mentor for HCWs and the study team
- At least one message every 3 weeks, to inquire about any issues and trigger a site visit if needed
- At least 1 visit every 10 weeks and at least 3 visits during the study period

% adherence _{intervention} = (number HF_s fulfilling intervention criteria above / total number of intervention HF)*100.

% adherence _{control} = (number HF_s fulfilling control criteria above / total number of control HF)*100%.

Descriptive statistics on the adherence will be provided by study arm (intervention and control).

The following are pre-defined major protocol violations at HF level with a direct bearing on the primary outcome :

Intervention HF:

Not having access to medAL-mentor for the HCWs or the study team during the entire study period

Control HF :

Having access to medAL-mentor for the HCWs and/or the study team any time during the study period

4.2. Analysis population definitions

Intention-to-treat analysis: This analysis includes all consultations in HF_s included in the study, regardless of whether the HCWs used ePOCT+ and had access to medAL-mentor.

Per-protocol population: This analysis includes only consultations in HF_s included in the study and that did not experience major protocol violation during the study period.

5. Trial population

5.1. Screening data

Screening data will be presented for all children visiting participating HF_s (see eligibility criteria below).

The total number of days recruiting, the total number of consultations with screened children and the total number of consultations with enrolled participants will be presented. The number of excluded participants from the primary and secondary outcomes analysis (with the number of those who did not provide consent and those without data available) will be presented. The summary will be provided overall and by HF.

5.2. Eligibility

5.2.1. Health facility eligibility

HF_s eligible for the medAL-mentor study are those included in the DYNAMIC study, and using ePOCT+ for the first time during the second phase of the DYNAMIC study :

- 20 HF_s that were in the control group during the first phase of DYNAMIC
- 20HF_s newly included for the second phase of the DYNAMIC study, selected purposively among HF_s eligible for the first phase

(see SAP phase 1 for details on HF selection)

5.2.2. HCWs eligibility

All clinicians working in sampled HFs will participate to the medAL-mentor study.

5.2.3. Participants eligibility

A child is eligible for the medAL-mentor study if:

- they visit a HF included in the medAL-mentor study

AND

- they meet the following inclusion criteria and none of the following exclusion criteria:

Inclusion Criteria:

- Aged 1 day (24 hours) to 14 years (inclusive)
- Presenting for an acute medical or surgical condition

Exclusion Criteria:

[figure not shown]
- Presenting for scheduled consultation for a chronic disease (e.g. HIV, TB, NCD, malnutrition)
- Presenting for routine preventive care (e.g. growth monitoring, vitamin supplementation, deworming, vaccination).

Eligibility criteria will be assessed using the routine registry. For the primary outcome measure, all eligible participants will be included in the analysis.

For secondary and exploratory outcomes, whose measurement is based on ePOCT+ data, only participants managed with the tool will be included in the analysis. In addition, participants whose caregiver was unavailable, unable or unwilling to provide oral consent will be excluded from the analysis.

5.3. Recruitement

A CONSORT flow diagram will be used to summarise the number of consultations with participants who were screened and enrolled and the number of consultations analysed for secondary and exploratory outcomes.

5.4. Baseline HF and patient characteristics

The following baseline cluster (HF) characteristics will be summarized by study arm:

- HF type (dispensary or health center) and region
- Access to GoT-HoMIS
- Average number of patients under 15 seen per month by HF
- Baseline % antibiotic prescription by HF (as reported in ePOCT+) in the month before the start of the study (May 2023)

The baseline patient characteristics that will be summarized by study arm, and for the overall study include:

- Demographics: sex (number and percentage); age (median and IQR), age groups 0-2 months, 2 months - 5 years, 5-14 years (number and percentage) (for all included participants)
- Medical history: Main reasons for consultation - fever, respiratory, gastrointestinal, ear/nose/throat/mouth or skin complaint (number and percentage) (for participants with ePOCT+ data)
- Basic measurements: weight for age (median and IQR) (for participants with ePOCT+ data)

No formal statistical comparisons of baseline data will be performed.

6. Analysis

6.1. Outcome definition

6.1.1. Primary outcome

Percentage of children prescribed an antibiotic in the intervention group (medAL-mentor) as compared to the control group (routine monitoring)

Outcome measure: Number of children for whom at least one systemic (oral or parenteral) antibiotic has been prescribed during consultation, over all eligible children, as reported by the HCWs in the routine registry

Timing and method of assessment: documented by the HCW at the end of the consultation, in the routine registry (day 0)

Analysis type: superiority

6.1.2. Secondary outcomes

All secondary outcomes are compared between the intervention (medAL-mentor) and control (routine care) arms (superiority analysis).

a. Uptake of ePOCT+

Percentage of consultations with eligible children performed with ePOCT+

Outcome measure: number of consultations completed with ePOCT+, over all consultations with eligible children as reported in MTUHA books

Timing and method of assessment: documented by the HCW during the consultation (medAL-reader) and at the end of the consultation (routine registry), at day 0

Analysis type: superiority

b. Quality of care indicators

• Percentage of children in whom key signs have been checked by HCWs

Number of children in whom each of the key signs (temperature, weight, MUAC, respiratory rate) has been checked by HCWs, over the total number of children for whom this was recommended, as reported by HCWs in ePOCT+

Timing and method of assessment: documented by the HCW during the consultation (medAL-reader) at day 0

Analysis type: superiority

- **Percentage of children for whom appropriate diagnostic tests have been performed by HCWs**

Number of children for whom each of the diagnostic tests (haemoglobin and malaria tests) has been performed by HCWs, over the total number of children for whom the diagnostic test was recommended, as reported by HCWs in ePOCT+

Timing and method of assessment: documented by the HCW during the consultation (medAL-reader) at day 0

Analysis type: superiority

6.1.3. Exploratory outcomes

All exploratory outcomes are compared between the intervention (medAL-mentor) and control (routine care) arms.

a. Antibiotic prescription over time (longitudinal analysis)

Outcome measure: number of children for whom at least one systemic (oral or parenteral) antibiotic has been prescribed during consultation, over all eligible children, every week of the study period, as reported by the HCWs in the routine registry

Timing and method of assessment: documented by the HCW at the end of the consultation (routine registry) at day 0

b. Antibiotic prescription in children managed with and without ePOCT+

Outcome measure: number of children for whom at least one systemic (oral or parenteral) antibiotic has been prescribed during consultation, over all eligible children, as reported by the HCWs in the routine registry for children managed with and without ePOCT+

Timing and method of assessment: documented by the HCW at the end of the consultation (routine registry) at day 0

c. Antibiotic prescription reported in ePOCT+ versus in routine data (data consistency)

Outcome measure: number of children for whom at least one systemic (oral or parenteral) antibiotic has been prescribed during consultation systemic as reported by the HCW in ePOCT+ over number of children for whom at least one systemic (oral or parenteral) antibiotic has been prescribed during consultation systemic as reported by the HCW in the routine registry

Timing and method of assessment: documented by the HCW during the consultation (medAL-reader) and at the end of the consultation (routine registry) at day 0

d. Completion of ePOCT+

Outcome measure: number of consultations completed with ePOCT+, over all consultations started with ePOCT+

Timing and method of assessment: documented by the HCW during the consultation (medAL-reader) at day 0

e. Appropriate case management for malaria

Outcomes measure:

- % of consultations with febrile children tested for malaria
- % of consultations with children with a positive malaria test prescribed an antimalarial
- % of consultations with children with a negative malaria test prescribed an antimalarial
- % of consultations with untested children prescribed an antimalarial

Timing and method of assessment: documented by the HCW during the consultation (medAL-reader) at day 0

f. Appropriate case management for acute respiratory infections

Outcomes measure:

- % of children with acute respiratory infection prescribed an antibiotic
- % of children with bacterial pneumonia prescribed an antibiotic
- % of children with viral pneumonia prescribed an antibiotic
- % of children with cough/common cold prescribed an antibiotic

Timing and method of assessment: documented by the HCW during the consultation (medAL-reader) at day 0

g. Appropriate case management for diarrhea

Outcomes measure:

- % of children with acute diarrhea prescribed zinc
- % of children with acute diarrhea prescribed an antibiotic

Timing and method of assessment: documented by the HCW during the consultation (medAL-reader) on day 0

6.2. Analysis methods

Analyses will follow CONSORT guidelines.¹⁹

All the analyses will be carried out using generalized linear mixed models (GLMM, more specifically the multilevel logistic regression model with fixed and random-effects) to account for the complex multi-level structure of the data (induced by the stratified cluster randomized procedure), with individuals measurements nested within HCWs, who are themselves nested within HFs, which in turn are nested within districts, and at the highest-level districts are nested

within regions.²⁰ For the primary outcome, available risk factors at the individual level will be age category, sex, and type of final diagnosis (gastro-intestinal, respiratory, skin, malaria, other). For secondary outcomes, available risk factors at the individual level will be age, sex, child presenting with fever, gastro-intestinal, respiratory, ear/nose/throat/mouth and/or skin problem. In addition, to account for the correlation between the two exposure groups induced by the stratification, all the analyses will be adjusted for the stratification factors used in the randomization and not already accounted for (i.e. attendance rate and use of GoT-HoMIS) in the multi-level structure. Finally, the analyses will be adjusted by the baseline antibiotic prescription at each HF.

A special random-effects structure will be used at the HF level to account for unmeasured heterogeneity of the intervention effect²¹ and confounding by cluster will be dealt with by separating within- and between-cluster effects using a partitioning method.^{22,23}

Interactions (i.e. effect modification) between covariables (at the individual level) and exposure (i.e. medAL-mentor vs control) will be introduced into the model as fixed-effects. Variable selection will be based on clinical relevance and not on statistical tests of significance; consequently, no correction for multiple testing will be applied.²⁴

To assess the impact of the intervention at the population level (i.e. the population averaged effect), the two marginal probabilities in the exposed and unexposed children will be computed by marginalization of the estimated conditional probabilities.^{25,26} Based on these marginal probabilities, the marginal relative risk and marginal risk difference will be computed. These marginal parameters quantify the average impact of the intervention in the whole population, and to assess the impact of the intervention in specific subgroups of children marginal probabilities will be also computed in the subpopulations defined by the risk factors detailed above.

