3.2. Sample size

The sample size was calculated to demonstrate an absolute reduction of 15% in antibiotic prescription in the intervention group, in a superiority analysis.

The intraclass correlation coefficient (ICC=0.08), the baseline antibiotic prescription (40%, in absence of medAL-mentor supervision), the cluster size (a conservative estimate of 80 patients/month/cluster, for 6 months), and the coefficient of variation for cluster sizes (0.6) were estimated from results of the first phase of the study. The duration (6 months) was chosen to consider the time required to induce change in HCWs' behavior and to evaluate their fatigue over time.

To have 80% power to detect an absolute difference of 15% of antibiotic prescription between the two arms, for a two-sided test at alpha of 0.05, we would require 13 clusters and 6240 participants per arm. Given the uncertainty in the estimation of the parameters used for the sample size calculation, the time estimated to induce change and in order to we decided to include all the available HFs, i.e. 20 clusters per arm.

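### The SAP sets a 5% test from a multilevel logistic model on 40 randomised facilities but names no small-sample method; with the usual maximum-likelihood Wald z fit, a simplified version of the model has a size of about 7.5%

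*SAP*

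**What the plan says.** SAP section 4 (Statistical principles): "All applicable statistical tests will be 2-sided and will be performed using a 5% significance level", with two-sided 95% intervals. SAP 3.1 and 3.3 randomise 40 facilities 1:1: "Randomization will be stratified by number of patients/week", and also by access to GoT-HoMIS.

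SAP 6.2 specifies a generalised linear mixed model, "more specifically the multilevel logistic regression model with fixed and random-effects". The levels run from individuals through health care workers to facilities, "which in turn are nested within districts, and at the highest-level districts are nested" within regions. The model is adjusted for both stratification factors, and "Finally, the analyses will be adjusted by the baseline antibiotic prescription at each HF". It also has a special facility-level random-effects structure and arm-by-covariate interactions, and "confounding by cluster will be dealt with by separating within- and between-cluster effects using a partitioning method". From the fitted model, "the marginal relative risk and marginal risk difference will be computed".

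The SAP does not say whether estimation is by maximum likelihood or a REML-type method. It also gives no reference distribution, degrees of freedom, small-sample correction, interval method for the marginal effects, or fallback if the model does not converge. Stata appears only in the abbreviation list. Protocol 10.3 concerns the Phase 1 trial and leaves further detail to a SAP.

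**The concern.** The arm effect varies only between facilities. Its precision therefore rests on 40 units, however many consultations are recorded, and each facility-level covariate uses one more degree of freedom. Logistic mixed models are ordinarily fitted by maximum likelihood with Wald z tests. That approach understates the between-facility variance, because it divides by 40 rather than by the residual degrees of freedom. It also uses a normal reference where a t is needed. Both errors narrow the interval.

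Two things are at stake. Under that default, a medAL-mentor effect would be declared more often than the stated 5%. And because the choice is open, it could be made after the result is seen.

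**Working it through.** **The plan's own sample size first.** Inputs from SAP 3.2: 40% versus 25%, 80% power, two-sided 5%, ICC 0.08, cluster size 80 × 6 = 480, coefficient of variation of cluster size 0.6.

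- Individually randomised size: 152 per arm.
- Design effect, equal clusters: 1 + 479 × 0.08 = 39.32. Clusters: 152 × 39.32 / 480 = 12.45.
- With a mixed-model relative efficiency of 0.992 for unequal sizes, the design effect is 39.32 / 0.992 ≈ 39.65, which gives 12.55 clusters.
- Both round up to 13, and 13 × 480 = 6,240. This reproduces the SAP's figure: "we would require 13 clusters and 6240 participants per arm".
- The more conservative form 1 + (1.36 × 480 − 1) × 0.08 = 53.1 would need 17 clusters.
- All of these use normal quantiles.

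**Facility-level parameters.** Intercept, arm, two stratification factors and baseline prescribing make p = 5, so df = 40 − 5 = 35. SAP 6.2 does not say which covariates are partitioned. If every dummy for age category (2), sex (1) and diagnosis type (4) gets a facility mean, p = 5 + 7 = 12 and df = 28.

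**Size of the nominal 5% test, large-cluster closed form.**

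- ML with z: P(|t_df| > 1.96 × √(df/40))
- ML with t: P(|t_df| > t_0.975,df × √(df/40))
- REML-type with z: P(|t_df| > 1.96)
- REML-type with t: 5% by construction

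At p = 5 the ML-z threshold is 1.96 × √(35/40) = 1.833 on the t(35) scale, where the correct value is 2.030.

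| Method | p = 5 | p = 12 |
|---|---|---|
| ML, z | 7.5% | 11.2% |
| ML, t | 6.6% | 9.8% |
| REML-type, z | 5.8% | 6.0% |
| REML-type, t | 5.0% | 5.0% |

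**Simulation check (null, logistic mixed model by ML, Wald z).** Settings: 40 facilities, mean size 480, CV 0.6, 40% prescribing, total logit variance about 0.08/0.24 = 0.33, 3,000 to 4,000 runs per setting.

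- Facility level only, p = 5: 7.3% and 7.4% in two separate simulations. With a smaller facility SD of 0.35 on the logit scale it was 8.4%.
- Health care worker level also fitted, p = 5: 8.2%, 7.1%, 7.4% and 5.2% when none, half, three quarters and all of the variance lies at that level.
- p = 12: 10.4% to 11.9%.
- ML variance rescaled by 40/df with a t reference, p = 5: 4.7% to 5.1%, but 3.2% if all variance is at health care worker level. At p = 12: 4.2% to 5.6%.

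The worker-level runs assumed 3.75 workers per facility, from 75 in the 20 Phase 1 intervention facilities (Protocol 10.2). The same section's Phase 2 figures, about 300 workers in 100 facilities, give 3.0. Not simulated: the interactions, the special random-effects structure, the marginal effects, and Kenward-Roger or permutation inference as such.

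**Cost in width and power.** Interval ratio at p = 5: (2.030/1.96) × √(40/35) = 1.107. For power with 9,600 per arm, SE = √((0.24 + 0.1875) × DE / 9,600).

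- DE 39.65: SE 0.0420, noncentrality 0.15/0.0420 = 3.57. Noncentral t(35) power is 95.6% beyond 1.833 (ML-z) and 93.5% beyond 2.030.
- DE 53.1: SE 0.0486, noncentrality 3.08. Power is 89.2% and 85.1%.

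**The case against.** The strongest reply is that 40 clusters is not few and that the design has slack: 20 facilities per arm against 13 required. At five parameters the two analyses disagree only when the t statistic lies between 1.83 and 2.03. Under the planned effect that chance is about 2% (95.6 − 93.5) or 4% (89.2 − 85.1). This stands, and it limits the severity. It does not protect the test when the effect is absent or small, which is the case the 5% level is meant to cover.

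Second, if the clustering is nearly all between health care workers, ML with z is close to 5% and the corrected test is conservative (3.2% in simulation). This also stands. The documents do not give the split, and at half or three quarters the size was still 7.1% to 7.4%.

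Third, SAP 6.2 cites methods papers that may imply an estimator. Those papers were not available here, and the SAP does not say that it adopts their estimator or test.

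A reader might infer that the trial's true type I error is 7.5%. The documents do not support that: the SAP does not commit to ML with z, and its model has terms that were not simulated. A reader might also infer that the district and region levels inflate the error. SAP 6.2 does not say that they are random, their effect on size is expected to be small, and a variance estimated at zero gives the same fit as leaving that level out.

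**Conclusion.** The omission is real. Its importance is minor to moderate. Nothing in SAP section 4 or 6.2 fixes the size of the primary test at the stated 5%. Under the ordinary fit for this class of model, the size is about 7.5% with five facility-level parameters and a facility intercept. It is near 5% if almost all clustering is at health care worker level, and about 11% if the partition adds a facility mean for all seven covariate dummies. These figures depend on the estimator, the variance split and the partitioned covariates, none of which the SAP states. They should be read as sizes for simplified models. The conclusion matters most for a p-value or confidence limit near the threshold.

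A separate, lesser matter is that Protocol 4.2 lists five districts or councils in two regions, and neither was a stratum in SAP 3.3. Two regions are too few to estimate a region variance reliably, if a random level is intended.

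**What to change.** State in SAP 6.2, before analysis, that the primary p-value and interval use a small-sample method, either:

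- a t reference with 40 minus the number of facility-level parameters as degrees of freedom, and a df-corrected or REML-type variance; or
- a permutation test that reproduces the stratified allocation, including the handling of misfits in SAP 3.3.

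Apply the same correction to the marginal relative risk and risk difference. List the covariates to be partitioned, because each facility mean uses one degree of freedom.

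As a minor addition, enter region as a fixed effect rather than a random level, and name a fallback for non-convergence. One option is a facility-level regression on arm, stratification factors, region and baseline prescribing with a t reference.

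The cost is SAP wording and standard software. The interval is about 11% wider than with ML and z at five parameters, and about 12% wider with a region term ((2.032/1.96) × √(40/34) = 1.125). The power loss is about 2 points at the design effect that matches the SAP's 13 clusters and about 4 at the conservative one. Both results stay above the 80% target. If clustering is almost wholly between health care workers, the test will be somewhat conservative.

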8.1.2 Management of sick children during the initial consultation

In HFs with dedicated staff for triaging patients, sick children will first be assessed by this person using the triage module of ePOCT+ in the tablet. If the child requires urgent treatment, the triaging person will immediately inform the attending HCW(s), so that she or he can give priority to that child over others waiting to be seen. If not, the child will queue normally and be attended by the next available HCW. As part of triage, the vital signs will be measured (temperature, respiratory rate, weight and MUAC) as well as, if the child fulfils certain clinical criteria, oxygen saturation and cardiac rate using the pulse oximeter. If there are no dedicated triage staff, the triage module will be deactivated and vital signs will be measured during the consultation.

The attending HCW will either manage the child using the ePOCT+ algorithm (in intervention facilities) or as per routine (in control facilities). If the child needs to go to another room for laboratory investigations (rapid tests or other), the HCW will be able to suspend the ePOCT+ algorithm and data recording in the tablet and attend another child in the meantime, opening a parallel session in the tablet. When the child returns with the test results, the HCW will resume the ePOCT+ algorithm and data recording of that child and continue the consultation normally. At the end of the consultation, the HCW, in both intervention and control facilities, will be asked to enter the final decision on referral, tests performed, final diagnoses and treatments prescribed (see chapter 8.1.6 on outcomes measurements). After the consultation, this information will be synced to the server at IHI offices as soon as there is internet connectivity.

Figure 9: Flowchart of health facilities and patients included in Phases 1 and 2

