2.3. Study objectives

The primary objective of the study is to determine whether the provision of medAL-mentor, an online monitoring and benchmarking tool, decreases antibiotic prescription by primary care clinicians using a clinical decision support algorithm (ePOCT+) for the management of sick children.

Secondary objectives are :

- a. To assess the impact of medAL-mentor on clinicians' uptake of ePOCT+
- b. To assess the impact of medAL-mentor on clinicians':
 - a. Performance of key measurements and assessment of signs by clinicians
 - b. Compliance with the recommendations related to point-of-care tests (for malaria and hemoglobin)

3. Study methods

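### The primary model for antibiotic prescribing adjusts for final diagnosis, which is made after randomisation and which mentoring may change, so the effect can be under- or overstated

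*SAP*

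**What the plan says.** SAP section 6.2 plans a multilevel logistic model for all outcomes. Its list of covariates for antibiotic prescribing reads: "available risk factors at the individual level will be age category, sex, and type of final diagnosis (gastro-intestinal, respiratory, skin, malaria, other"). The models for the secondary outcomes use age, sex and presenting problem instead. All analyses are also adjusted for the stratification factors and for each facility's baseline prescribing. The section continues: "Interactions (i.e. effect modification) between covariables (at the individual level) and exposure (i.e. medAL-mentor vs control) will be introduced into the model as fixed-effects". Covariates are selected on clinical relevance, with no rule against post-randomisation variables. It adds that "confounding by cluster will be dealt with by separating within- and between-cluster effects using a partitioning method", without saying which covariates are partitioned.

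For the population-level effect, "the two marginal probabilities in the exposed and unexposed children will be computed by marginalization of the estimated conditional probabilities", and the marginal relative risk and risk difference follow from these. For subgroups, "marginal probabilities will be also computed in the subpopulations defined by the risk factors detailed above". The distribution of diagnoses used in the averaging is not given. No primary or sensitivity analysis without final diagnosis is specified.

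**The concern.** The primary objective (SAP section 2.3) is whether providing medAL-mentor decreases prescribing. That is a total effect, including any part that works by changing what the health worker diagnoses. Facilities are randomised first; the diagnosis is made later by staff who are, or are not, receiving feedback.

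The SAP itself allows that mentoring may change what leads to the diagnosis. Its secondary objectives cover uptake of ePOCT+, assessment of signs and "Compliance with the recommendations related to point-of-care tests (for malaria and hemoglobin"). Malaria is one of the five diagnosis categories. The parent protocol treats final diagnosis as a product of the consultation: in section 8.1.2 the health worker "will be asked to enter the final decision on referral, tests performed, final diagnoses and treatments prescribed" at its end, and section 7.1 lists the distribution of final diagnoses among the Objective 1 outcomes.

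If mentoring moves children between categories with different prescribing rates, holding diagnosis fixed discards that part of the effect. If unmeasured severity drives both diagnosis and prescribing, conditioning on diagnosis adds a second bias. The primary result would also depend on an averaging choice made after the data are seen.

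**Working it through.** **The plan's own figure.** SAP section 3.2 takes 40% against 25%, ICC 0.08 and 80 × 6 = 480 children per facility. Individual randomisation needs 152 per arm (two-sided 5%, 80% power). The design effect is 1 + 479 × 0.08 = 39.32, and 152 × 39.32 / 480 = 12.45, so 13 clusters and 13 × 480 = 6240 per arm, as stated. Allowing for the size variation (CV 0.6) by relative efficiency gives 39.65 and 12.55, again 13. No covariate enters, so removing diagnosis leaves the sample size unchanged.

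**Inputs for the bias calculation.** From the SAP: control prescribing 40% and a true difference of −15 points. Assumed, because the documents give no values:

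- Control mix: gastro-intestinal 20%, respiratory 40%, skin 10%, malaria 10%, other 20%.
- Prescribing *g* points higher in respiratory than in malaria (*g* = 20, 40, 50), with the other three categories midway at *x*.
- Mentoring shifts *s* points from respiratory to malaria.

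The control average is 0.5*x* + 0.4(*x* + *g*/2) + 0.1(*x* − *g*/2) = *x* + 0.15*g* = 40, so *x* = 40 − 0.15*g*. A common arm odds ratio is then solved so that the intervention arm totals 25% over its shifted mix.

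**Two ways to average.** Own-arm: Σ mix₁p₁ − Σ mix₀p₀. Common mix: Σ ½(mix₀ + mix₁)(p₁ − p₀).

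**Worked case, *g* = 40, *s* = 5.** Control prescribing is 54% (respiratory), 14% (malaria) and 34% (the rest). The solved odds ratio is 0.52, giving 37.90%, 7.80% and 21.13%.

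- Own-arm: (0.5 × 21.13 + 0.35 × 37.90 + 0.15 × 7.80) − 40 = 25.0 − 40 = −15.0.
- Common mix: 0.5 × (21.13 − 34) + 0.375 × (37.90 − 54) + 0.125 × (7.80 − 14) = −13.2.

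**All cases (true difference −15.0 throughout).**

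| Shift *s* | Common mix, *g* = 20 | *g* = 40 | *g* = 50 | Conditional OR, *g* = 40 |
|---|---|---|---|---|
| −5 | −15.9 | −16.7 | −17.1 | 0.44 |
| 0 | −15.0 | −15.0 | −15.0 | 0.48 |
| 2 | −14.7 | −14.3 | −14.1 | 0.49 |
| 5 | −14.1 | −13.2 | −12.8 | 0.52 |
| 10 | −13.2 | −11.4 | −10.5 | 0.57 |

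Own-arm averaging gives −15.0 in every cell. Under a common mix, a shift of 2 loses 2–6% of the effect, 5 loses 6–15% and 10 loses 12–30%; the reverse shift of 5 overstates it by 6–14%. The marginal odds ratio is (25/75)/(40/60) = 0.50, so 0.48 at no shift reflects non-collapsibility; the movement from 0.44 to 0.57 for one and the same total effect comes from the shift.

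**With unmeasured severity.** A second, two-category calculation let severity affect both diagnosis and prescribing, with assumed shifts of 15–20 points in one severity group. The common-mix difference departed from the total by +1.9 to +4.2 points when respiratory labels fell and by −1.8 to −2.4 when they rose. With no direct arm effect the sign could reverse (total −1.2, adjusted +1.8). Own-arm averaging again returned the total.

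**Precision without diagnosis.** A simulation of 40 facilities (480 children each, ICC 0.08, 80 baseline children, 2,000 replicates per setting) varied facility case-mix SD (5, 10, 15 points) and the stability of residual prescribing from baseline (correlation 0.3, 0.6, 0.8). With baseline prescribing in the model, dropping the facility diagnosis mix changed the standard error of the arm effect by −2% to +7%. The largest loss arose when case-mix explained 29% of between-facility variance and the correlation was 0.3.

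**The case against.** The marginal relative risk and risk difference are the population-level measures the SAP names, and averaging each arm over its own children is a natural reading of section 6.2. Under that reading the estimate is not affected. This stands as a possibility, but the same section speaks of the average impact in the whole population, which equally allows a common mix. The arm coefficient and the diagnosis-defined subgroup effects are unprotected either way.

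The factors are called available and are chosen on clinical relevance, so inclusion is planned rather than absolutely fixed. Nothing in the SAP would exclude diagnosis, however.

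The mechanism may be weak. Both arms have ePOCT+ and the same stewardship training, malaria tests are routinely available, and relabelling bacterial as viral pneumonia stays within respiratory. The protocol passages describe tablet entry and DYNAMIC outcomes, not the routine registry that supplies this primary outcome. These points limit the likely size; they do not make diagnosis a baseline variable.

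The largest losses need extreme inputs: a 10-point shift doubles malaria diagnoses, and a 50-point gap puts control prescribing in malaria at 7.5%. After a 5-point shift, power with 20 facilities per arm is 92% to 85% against 95% with no shift (design effect 39.65), or 82% to 74% against 87% with the conservative 1 + (1.36 × 480 − 1) × 0.08 = 53.14. The trial would usually still detect an effect.

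Finally, diagnosis is the only clinical case-mix variable listed for the primary outcome. Presenting complaint is summarised only "for participants with ePOCT+ data" (SAP section 5.4), and the regions differ in malaria endemicity. This is a real reason for choosing diagnosis, and chance imbalance across 40 facilities is possible. It is a cost of the change, not a reason to condition on a variable the intervention may move.

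**Conclusion.** The concern holds and should be fixed. Final diagnosis is a post-randomisation variable that mentoring may change, and it is a planned term in a model whose target is a total effect. The status of the variable is certain. The size of any bias is not, because the documents give neither a diagnosis mix nor an expected shift. On the assumptions above it ranges from nil, through about 1 to 2 points of 15 in either direction for a 5-point shift, to 4.5 points for the most extreme case. It is nil if the five broad categories do not move or children are only relabelled within respiratory, and for the risk difference also if each arm is averaged over its own diagnoses. Which of these applies cannot be known when the SAP is fixed, so the primary model should not depend on it. If diagnosis is among the partitioned covariates, the facility diagnosis mix also enters at the randomised level.

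**What to change.** In SAP section 6.2, remove final diagnosis, its interaction with arm and any partitioned facility mean of it from the primary-outcome model. Keep age category, sex, the stratification factors, facility baseline prescribing and the planned multilevel structure. Report prescribing by final diagnosis as exploratory, stating that it conditions on a post-randomisation variable. State the distribution over which marginal probabilities are averaged. If a model with diagnosis is kept as a sensitivity analysis, average each arm over its own children.

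The cost is about two sentences, with no new data and no change to the sample size. The price is the lost case-mix adjustment and a possible small loss of precision, only partly offset by baseline prescribing and the region and district levels.
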